Study Population: A total of 240 HIV-exposed but uninfected (HEU) and 240 HIV un-exposed uninfected Malawian and Ugandan infants and their caregivers recruited in the Promoting Maternal and Infant Survival Everywhere Neurodevelopmental follow-up study (PROMISE ND) sites at Malawi College of Medicine-Johns Hopkins University (MCM-JHU), Blantyre, Malawi; and at Makerere University–Johns Hopkins University (MU-JHU), Kampala, Uganda respectively. In addition, 120 HIV infected (HIV+) children and their caregivers will be recruited from affiliated health clinics at both Malawi and Uganda sites.

Sample size: A total sample size of 600 children and their caregivers in two study sites (n=300 per site) will be included in this study

Study duration: Approximately 5 years.

Overall goal: This research will adapt and validate BPG as a measure of cognitive performance in school-age children as both a static (1 session of BPG) and dynamic assessment (12 training sessions of BPG)

Aims and objectives:

Aim1: To adapt and evaluate the concurrent and predictive validity of BPG as a static (baseline) and dynamic (during 12 training sessions) cognitive assessment at the Malawi and Uganda sites.

Objective 1.1 To evaluate whether BPG static (baseline) assessment corresponds to the gold standard static measures previously adapted to HEU, HUU, and HIV+ study cohorts at Uganda and Malawi country sites (KABC-II, TOVA, CogState).

Aim2: To compare the validity of BPG static and dynamic assessments.

Objective 2.1 To evaluate the correspondence of BGP-based static and dynamic assessments of the cohorts' prior early childhood longitudinal trajectories (KABC-II), considering the effect of proximal (e.g. HIV status) & distal (height, weight, HIV disease factors, demographic) risk factors causing developmental delay and cognitive problems.

Aim3: To test the sensitivity of dynamic assessment to learning loss over time by evaluating how much BPG performance gains diminish during a 6-month absence of training

Objective 3.1 To assess change over time in KABC-II, TOVA and CogState scores (learning loss) 6 months after the children complete 12 sessions of BPG training, overall and by cohort.

Study Outcomes:

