5.0 NEURODEVELOPMENTAL ASSESSMENT PROTOCOL DESIGN

5.1 Overview of Study Design:

[figure not shown]
Static and Dynamic Assessment Process for Each Study Child. Figure 6 provides an overview of study visits and assessments. Following enrollment and physical and medical exams, each child will return to the clinic with their principal caregiver for a half-day of gold standard neuropsychological assessments (KABC-II, TOVA, CogState). At this time the caregiver will complete the Achenbach CBCL questionnaire for school-age children, the Caldwell HOME scale, the SES material possessions evaluation, and the Hopkins Symptom Checklist-25 (caregiver psychological well-being). We will explain assessments and provide instructions in the local language. Study assessments will proceed in two phases. In Phase I, children will be randomized to start BPG trainings (50% of sample) or to a wait-list condition. Within a week after baseline assessment, the full sample of children will be contacted by a field research assistant and facilitate a first BPG session. This first session will be completed by the full sample because it will be considered as an internal performance evaluation session with BPG and will be completed on a tablet, supervised by the field research assistant. This will be done as part of the 50-60 minutes training session on the 5 BPG games (about 10 minutes per game), and will constitute the BPG static assessment. Thereafter, the field research assistant will return with children allocated to the BPG trainings (50% of sample) at a convenient time and supervise BPG training several times per week until 12 training sessions are completed. The 12th session internal evaluation performance measures for the 5 core games and one added EF game will provide the endpoint for BPG dynamic assessment (gain in BPG performance from session 1 to session 12). Because BPG training will occur on a tablet connected to the internet through the mobile network, performance data can be uploaded for analysis via the MSU GEL lab principal server, as done in the Kayunga Uganda CCRT study with BPG ¹.

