Post Testing and 6-month BPG Dynamic Assessment Follow-up. Within 2-4 weeks after completing BPG training and dynamic assessment, the full sample of children and their caregivers will return to the clinic for a full gold standard neuropsychological evaluation as the caregiver once again completes the CBCL. The final step in Phase I of our study process will be when the field research assistant returns with the child one final time after 6 months to administer 1 session of the BPG games to the full sample (corresponding to an internal performance evaluation for one final time). Within 2-4 weeks of this final BPG assessment, all children and their caregivers will return to the clinic for a gold standard neuropsychological evaluation. Our rationale for choosing when to have the final assessment is based on past work: after 6 months without training, the benefits of training may begin to diminish in terms of a slower rate of change in comparison to the rate of change during the training period. This BPG performance change from post training to 6-mo follow-up will provide an additional dynamic outcome for validity analyses.

In Phase 2 of the study we will assess the static and dynamic properties of an executive behavior-focused cognitive rehabilitation game package called Village Builder. In this Phase, children allocated to the wait-list condition will complete 12 sessions of training with Village Builder in a mobile device and facilitated by a research assistant. Within 2-4 weeks of the final Village Builder session, children will attend the clinic for a gold standard neuropsychological evaluation using the same battery of tests as in Phase 1. The last visit of Phase 2 will be 6 months (+/- 4 weeks) after completion of the training, where a final session of Village Builder will be administered (static evaluation) along with the battery of neuropsychological tests. Caregivers will also complete the CBCL, SES and HOME assessments in the same study visits as their children.

Figure 6. Study visits and assessments (numbers for 1 site shown)

PHASE I

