Unlike the existing games in Africa BPG that emphasize vigilance attention, monitoring and working memory, and visual spatial learning and navigation (mazes task), this new Village Builder game will emphasize executive function and reasoning in children. It will be intuitive, culture-fair, non-violent, and designed to be engaging for the computer novice and casual gamer. [name] has served as a consultant on NIH application to develop a touch screen Android Tablet assessment game package for assessment of executive functioning in preschool-age children, called "EF Touch". This app has undergone pilot testing with Kenyan children 4 to 6 years of age.⁶³ Using a model of EF development based on self-control interventions, pro-social values, and validated in early and middle childhood in terms of social and academic outcomes,⁶⁴ [name], [name], and [name] will work together to incorporate the best validated response features of EF Touch (Animal Go/No-Go, Silly Sounds Stroop, Pick the Picture)⁶³ into the new Village Builder EF game. The eventual goal is to compare the dynamic versus static BPG cognitive assessment features when they emphasize attention, memory, and learning tasks and when they emphasize planning and reasoning tasks in school-age children. Both types of BPG games (attention/memory/learning versus planning/reasoning) will also be compared to the gold standard of tests presently validated for the study sites (KABC/TOVA/CogState) in terms of their comparative sensitive to more proximal (HIV exposure and treatment) and distal (nutrition and quality of caregiving and home environment)

risk factors.

By comparing Village Builder executive function (EF) game to the existing Africa BPG package, we can better understand what value it adds in terms of a static and dynamic assessment of brain/behavior function in younger school-age African children. At present, no such CCRT intervention or assessment program exists that has been validated for African children, despite the great importance of EF in frontal lobe brain development at this stage of middle childhood. EF and frontal lobe development are vitally important precursors for future neurocognitive adaptation and function in children affected by HIV (e.g., self-management, impulsivity, planning, treatment adherence, psychosocial adjustment and prosocial behavior) as they age into adolescence and eventually into early adulthood.

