5.6.6 Summary of Procedures by Study visit

The following procedures will be conducted at the screening and enrollment visit of all enrollees

Table 1: Enrollment and Intake Visit(s) for all enrollees

Component	Procedures
Administrative and Regulatory	
 • Assess eligibility • Obtain written informed consent/ assent • Assign a Participant Identification (PTID) Number • Provide reimbursement for study visit
Clinical	
 • Obtain medical history • Conduct a brief physical examination (main organ systems and
Neurodevelopment Assessments	KABC-II TOVA
Caregiver-reported assessments	CBCL HOME
Brain Powered Games	1 st session for treatment condition (e.g. training) and only 1 session for wait list group (e.g. assessment)

*Depending on staff availability and scheduling, enrollment and baseline visits will be done on the same day

Table 2: BPG training visits for 50% of sample

Component	Procedures
Administrative and	
 • Schedule next visit
Brain Powered Games package	
 • Complete 10 sessions (About 2 per week for 6 weeks) of approximately 30-45 min

Table 3: Follow-up Visits for all enrollees

Component	Procedures
Administrative and	
 • Provide reimbursement for study visit

Clinical	
 • Obtain medical history • Conduct a brief physical examination (main organ systems and
Neurodevelopment Assessments	KABC-II TOVA
Caregiver-reported assessments	CBCL HOME
Brain Powered Games	12th session for BPG training group and 1 session for wait list group 1 session at 6-months follow-up for entire sample

Table 4: 12 session trainings of Village Builder (wait-list) and

Component	Procedures
Administrative and	
 • Provide reimbursement for study visit
Clinical	
 • Obtain medical history • Conduct a brief physical examination (main organ systems and
Neurodevelopment Assessments	KABC-II TOVA
Caregiver-reported assessments	CBCL HOME
Village Builder	
 • Complete 12 sessions (About 2 per week for 6 weeks) of approximately 30-45 min

Table 5: Follow-up visits for wait-list group

Component	Procedures
Administrative and	
 • Provide reimbursement for study visit

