Clinical	
 • Obtain medical history • Conduct a brief physical examination (main organ systems and
Neurodevelopment Assessments	KABC-II TOVA
Caregiver-reported assessments	CBCL HOME

Village Builder	
 • 1 session at 6-months follow-up
-----------------	---

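### The only Village Builder session labelled static comes six months after 12 training sessions, which does not match the untrained session used as the BPG static score

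*Combined protocol and SAP*

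**What the plan says.** Section 5.1 gives the purpose of Phase 2: "we will assess the static and dynamic properties of an executive behavior-focused cognitive rehabilitation game package called Village Builder". The schedule is then that "children allocated to the wait-list condition will complete 12 sessions of training with Village Builder", a gold-standard battery follows 2-4 weeks after the last of these, and a closing visit takes place six months (plus or minus four weeks) after training, "where a final session of Village Builder will be administered (static evaluation) along with the battery of neuropsychological tests". The visit tables in section 5.6.6 agree on the counts. Table 4 has "Complete 12 sessions (About 2 per week for 6 weeks) of approximately 30-45 min" and Table 5 has "1 session at 6-months follow-up". Neither table labels a session static or dynamic, and neither lists a separate Village Builder evaluation before training.

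For BPG, section 5.1 says that the first session, played by the full sample within a week of the baseline battery, "will constitute the BPG static assessment". The dynamic measure is the change between sessions 1 and 12. The BPG session after six months without training is described as giving a further dynamic outcome. The aims in the Schema and in section 5.2.2 attach the word baseline to static.

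Section 5.6.5 says that by comparing Village Builder with the existing package "we can better understand what value it adds in terms of a static and dynamic assessment of brain/behavior function".

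**The concern.** The same point in the design, one session after six months without training, is a dynamic outcome for BPG and the static evaluation for Village Builder. An analyst who follows the Phase 2 text would take a 13th-exposure score as the Village Builder static measure and set it beside a first-exposure BPG score. Any difference in static validity between the two games would then mix the type of game with the amount of training. Within Village Builder, the static score would carry part of what the dynamic score is supposed to isolate.

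If the analyst uses session 1 instead, the readable text does not say which gold-standard battery is its concurrent criterion. For BPG that link is explicit and the interval is at most a week. Section 7.1.2 contains no Village Builder analysis, so the labels in section 5.1 are the only guidance. Section 3.0 attaches a hypothesis about the executive function game to Aim 2, so the comparison will be looked at.

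**Working it through.** The plan states no figure on this point. The check compares the definitions, with two counts and one identity.

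**Definitions side by side**
- *Static, BPG:* session 1, before training (section 5.1).
- *Static, Village Builder:* the only session given the label is the six-month session (section 5.1).
- *Dynamic, BPG:* session 1 to session 12 gain, plus the change from post-training to six months (section 5.1).
- *Dynamic, Village Builder:* not defined.
- *Battery nearest the static session, BPG:* the baseline battery, within a week (section 5.1).
- *Battery nearest session 1, Village Builder:* the last battery timed before it is the Phase I final battery, at an unstated interval. The first one timed in Phase 2 comes 2-4 weeks after session 12.

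**Exposure count.** 12 training sessions + 1 session at six months = 13 Village Builder sessions per wait-list child. Session 1 is untrained on Village Builder; the session labelled static is the 13th.

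**Children affected.** Section 5.6.1 assigns 60 HEU, 60 HUU and 30 HIV+ children to the wait list: 60 + 60 + 30 = 150. The lists run to 120, 120 and 60, which are the per-site targets in sections 5.4 and 5.6, so I read them as per site: 2 × 150 = 300, the whole Phase 2 sample.

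**What the labelled score contains.** Write S1, S12 and S13 for the Village Builder scores at those sessions. Let D = S12 − S1 be the training gain and L = S12 − S13 the loss over six months. Then

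S13 = S12 − L = S1 + D − L.

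The labelled static score is therefore the untrained score plus whatever part of the gain is retained. It equals S1 only if the retained gain D − L is zero. The BPG static score is S1 alone.

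**Why no direction follows.** For a criterion C,

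corr(S13, C) = [cov(S1, C) + cov(D − L, C)] / [SD(S13) × SD(C)].

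Moving from S1 to S13 changes the numerator by cov(D − L, C) and also changes SD(S13). The documents give neither quantity for Village Builder. Retained learning could raise the correlation with the gold standard, or training could compress scores and lower it.

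**Could Phase I supply a Village Builder baseline?** Not from the readable text. Section 5.1 lists five games at session 1 and adds an executive function game only at session 12. The same section gives Village Builder training only to the wait-list group in Phase 2. Those two statements also need reconciling.

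**The case against.** The strongest reply is that nothing is missing. Session 1 of the 12 is untrained on Village Builder. Sections 1.0 and 5.6.5 describe monitoring of performance at each training session and recording of game play. Those statements are made for BPG, but Village Builder is described in the same section and section 5.3 lists a BPG executive function game. This stands. A reader might infer that Village Builder has no untrained score, or that its static-versus-dynamic question cannot be answered; the documents do not support either.

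Second, static is used loosely. The Schema's overall goal speaks of "both a static (1 session of BPG) and dynamic assessment (12 training sessions of BPG" without requiring an untrained session. Section 2.9 defines static as a single session, and section 7.1.2 applies the word to a one-month post-training BPG score. The Phase 2 label may mean no more than a single-session evaluation. This weakens the contradiction but does not remove it, because section 7.1.2 pairs the post-training score with an intake static score and Village Builder has no designated counterpart.

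Third, a reader might size the effect from Table 1 in section 4.1, where correlations with post-training MPI exceed those with pre-training MPI by 0.05 to 0.08 on all seven rows (for example 0.37 − 0.32 = 0.05 and 0.47 − 0.39 = 0.08). That table does not bear on the question. It holds the game measure fixed and changes the date of the criterion, whereas here the date of the game score changes. Its measures are means and slopes over 12 sessions of another product, in survivors of severe malaria.

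Fourth, Figure 6 and the schedules in the appendices are not readable, and Table 4 lists KABC-II and TOVA without timing. A battery close to session 1 may be specified there, so it would be too strong to say that none exists or that the criterion is months old.

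Finally, the primary outcome in section 5.3 concerns BPG, Village Builder is not named in the aims and objectives of section 5.2.2, and section 5.6.5 describes the comparison across types of game as an eventual goal. This limits the stakes.

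**Conclusion.** The point holds as a conflict of definitions. In the readable text the one Village Builder session designated static follows 12 training sessions and six months without training, while its BPG counterpart is the untrained first session. Used as labelled, it would make the static comparison between the games unlike-for-unlike for every wait-list child (300, on the per-site reading). No bias direction or magnitude can be stated.

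The conclusion rests on three assumptions: that Figure 6 and the appendix schedules do not already settle the labels; that Village Builder records performance at each session as BPG does; and that untrained means untrained on this game. On the last, Tables 1 and 3 of section 5.6.6 give wait-list children three earlier single BPG sessions (1 at intake + 1 at post-testing + 1 at six months = 3). The BPG primary outcome is not affected. The definitions should be settled before Phase 2 scores are analysed, so that the static score is not chosen after the data are seen.

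**What to change.** In the Phase 2 paragraph of section 5.1 and in Tables 4 and 5 of section 5.6.6:

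1. Name Village Builder session 1 as the static assessment.
2. Name the session 1 to session 12 gain as the dynamic assessment.
3. Relabel the six-month session as the retention measure, in line with the six-month BPG session in Phase I.
4. Name the Phase I final battery as the concurrent criterion for session 1. Where feasible, schedule session 1 within a stated short window of that battery, for example the 2-4 weeks used elsewhere in section 5.1. Otherwise record the interval and adjust for it.

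The cost is a few lines of wording and a scheduling rule. No visit, test or session is added. The small downside is less freedom over when a child starts Phase 2; the record-and-adjust option covers sites that cannot keep to the window.

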5.2 Study goals, aims and objectives

5.2.1 Study Goal

The overall goal of this research is to adapt and validate BPG as a measure to assess cognitive changes as a child plays with BPG once (static assessment) and over the course of 12 training sessions (dynamic assessments of cognitive change over time).

5.2.2 Aims and objectives:

Aim 1: To adapt and evaluate concurrent and predictive validity of BPG static (baseline) and dynamic (during 12 training sessions) cognitive assessments at the Malawi and Uganda sites.

Objective 1.1 To evaluate whether BPG static (baseline) assessment corresponds to the gold standard static measures previously adapted to HEU, HUU, and HIV+ study cohorts at Uganda and Malawi country sites (KABC-II, TOVA, CogState).

Aim 2: To compare the validity of BPG static and dynamic assessments.

Objective 2.1 To evaluate the correspondence of BGP-based static and dynamic assessments the cohorts' prior early childhood longitudinal trajectories (KABC-II), considering the effect of proximal (e.g. HIV status) & distal (height, weight, HIV disease factors, demographic) risk factors causing developmental delay and cognitive problems.

Aim 3: To test the sensitivity of dynamic assessment to learning loss over time by evaluating how much BPG performance gains diminish during a 6-month absence of training

Objective 3.1 To assess change over time in KABC-II, TOVA and CogState scores (learning loss) 6 months after the children complete 12 sessions of BPG training, overall and by cohort.

5.3 Study Outcomes and Exposure Variables of Interest

Primary Outcome: Correlation between coefficients of gold-standard measures (KABC-II, TOVA, CogState) and BPG scores. We will evaluate the concurrent validity by computing correlation coefficients of the BPG and "gold standard" measures at intake, 1 and 7 months after intake.

Exposure Variables of Interest:

BPG package

BPG executive function reasoning/planning game (to be developed)

HIV status (infected, exposed, unexposed)

Nutritional and growth history (PROMISE NeuroDev R01 HEU and HUU cohorts)

ARV exposure and clinical response to treatment history (HIV cohort)

5.4 Recruitment

Six hundred African children will be recruited into this study at Clinical Research Sites in Kampala, Uganda and Blantyre, Malawi (n=300/site). These will include 120 HIV infected children from affiliated clinics serving children living with HIV; 240 HEU children from PROMISE study, and 240 HUU children from PROMISE ND study of

similar age group. We will enroll roughly equal numbers of boys and girls, but will not be powered to detect statistically significant differences between them.

Enrollment for the HEU and HUU Cohort

All HIV-exposed but uninfected (HEU) children from the Promoting Maternal and Infant Survival Everywhere Neurodevelopment follow-up (PROMISE ND R01 study) in Blantyre, Malawi (N=188) and Kampala, Uganda (N=208) study sites will be eligible for enrollment for our study since during Year 1 they will be 5 years and older (mean age at both sites 6.6 years, range 5.4-7.7 years). Our target enrollment for this proposal of 120 HEU children from each site (total HEU sample of n=240) during the study's first 2 years that can be easily obtained as it represents 60% of the HEU PROMISE ND cohort at both sites. Our HUU cohort will also consist of 120 HUU children at each study site (total HUU sample of n=240) and will also be recruited from the PROMISE ND cohort study, comprised of 178 HUU children in Malawi and 195 in Uganda. Our target enrollment of HUU children of 120 at each of these two sites is feasible given that it represents 64% of the PROMISE ND cohort and children will be within the required age range (mean age at both sites 6.2 years, range 4.9-7.4 years). In total, 240 HEU and 240 HUU children will be enrolled for the present study.

The great advantage to enrolling the HEU and HUU cohorts in the present study is that they have been assessed with the Mullen Scales of Early Learning (MSEL) at 12, 24, and 48 months of age and are being evaluated with the KABC-II at 48 and 54 to 60 months of age. Thus, we can rigorously establish their neurodevelopmental trajectory with the MSEL across 3 longitudinal time points and relate that trajectory to BPG static and dynamic outcomes respectively in terms of correspondence validity. We can do this while both controlling for and evaluating independently the BPG neurocognitive outcomes as affected by health history, hematology/CBC, neurological exam, and physical growth measures — more distal factors that are typically strongly related to neurocognitive function, and which should be adjusted for (see Figure 1; Section 2.8).

In the unlikely scenario that recruitment target numbers are not met and/or PROMISE ND participants cannot be traced, we will recruit from study roasters affiliated with MUJHU and Blantyre sites.

Enrollment for the HIV-Positive Cohort

For the children to be enrolled in the HIV cohort at each site, several hundred children across both sites living with HIV attend routine appointment at Kampala MUJHU and Blantyre JHU sites. We will approach the parents/caregivers to get permission to screen their children for eligibility. After obtaining informed consent, we will administer a baseline assessment including detailed medical histories and as much data as possible on age of HIV diagnosis and ARV initiation and treatment history, previous hospital admissions, diagnosis of opportunistic infections and ART initiation, regimens, side effects, and adherence. We will also obtain detailed standardized medical, hematological, immunological, and neurological information from these children. The children will then undergo the same gold standard (KABC-II, TOVA, CogState) and BPG assessment and training procedures as all other participating HEU and HUU children.

In case the sample size for the HIV cohort is not reached within affiliated health clinics, we will recruit from children that graduated from the P1104s study in both Uganda and Malawi. The P1104s study was an observational multicenter longitudinal study aiming to compare neuropsychological outcomes between the perinatally HIV+, HEU and HU children in sub-Saharan Africa. Children and their caregivers were recruited from the IMPAACT P1060 study. [name] served as protocol chair for the P1104s study. Potentially recruiting from these cohorts of HIV children is advantageous given their full neurodevelopmental characterization and medical data available.

